### 12.13.2.2 Female Patients

Female patients of childbearing potential are eligible to participate if they agree to use a highly effective method of contraception consistently and correctly as described in the [Table 13-1](#) below. Contraception guidance is to be followed during the time frame in [Section 6.1](#) on inclusion criteria. Refrain from donating eggs during the same time period.

**Table 13-1: Highly Effective Contraceptive Methods**

Highly Effective Contraceptive Methods That Are User Dependenta Failure rate of < 1% per year when used consistently and correctly.

Combined (estrogen and progestogen containing) hormonal contraception associated with inhibition of ovulationb
 
 
• Oral
 
• Intravaginal
 
• Transdermal
 

Progestogen only hormonal contraception associated with inhibition of ovulation
 
 
• Oral
 
• Injectable
 

Highly Effective Methods That Are User Independenta

Implantable progestogen only hormonal contraception associated with inhibition of ovulationb
 
 
• Intrauterine device
 
• Intrauterine hormone-releasing system
 
• Bilateral tubal occlusion
 

Vasectomized partner A vasectomized partner is a highly effective contraception method provided that the partner is the sole male sexual partner of the FCBP and the absence of sperm has been confirmed. If not, an additional highly effective method of contraception should be used.

**Sexual abstinence**

*Sexual abstinence is considered a highly effective method only if defined as refraining from heterosexual intercourse during the entire period of risk associated with the study treatment. The reliability of sexual abstinence needs to be evaluated in relation to the duration of the study and the preferred and usual lifestyle of the patient.*

**NOTES:**

- a) Typical use failure rates may differ from those when used consistently and correctly. Use should be consistent with local regulations regarding the use of contraceptive methods for patients participating in clinical study.
- b) Hormonal contraception may be susceptible to interaction with the study treatment, which may reduce the efficacy of the contraceptive method. In this case, two highly effective methods of contraception should be utilized during the treatment period and for 90 days after the last dose of study treatment

Abbreviations: FCBP=female of childbearing potential.

Pregnancy testing will be performed as outlined in the SoA (see [Section 2](#)).

### **12.13.3 Collection of Pregnancy Information**

#### ***12.13.3.1 Male Patients With Partners Who Become Pregnant***

The investigator will attempt to collect pregnancy information on any male patient's female partner who becomes pregnant while the male patient is in this study. This applies only to male patients who receive study treatment.

[figure not shown]
After obtaining the necessary signed informed consent from the pregnant female partner directly, the investigator will record pregnancy information on the appropriate form and submit it to the sponsor within 24 hours of learning of the partner's pregnancy. The female partner will also be followed to determine the outcome of the pregnancy. Information on the status of the mother and child will be forwarded to the sponsor. Generally, the follow-up will be no longer than the time period described in [Section 9.4.3](#) following the estimated delivery date. Any termination of the pregnancy will be reported regardless of fetal status (presence or absence of anomalies) or indication for the procedure.

#### ***12.13.3.2 Female Patients Who Become Pregnant***

[figure not shown]
The investigator will collect pregnancy information on any female patient who becomes pregnant while participating in this study. Information will be recorded on the appropriate form and submitted to the sponsor within 24 hours of learning of a patient's pregnancy. The patient will be followed to determine the outcome of the pregnancy. The investigator will collect follow-up information on the patient and the neonate, and the information will be forwarded to the sponsor. Generally, follow-up will not be required for longer than the time period described in [Section 9.4.3](#) beyond the estimated delivery date. Any termination of pregnancy will be reported, regardless of fetal status (presence or absence of anomalies) or indication for the procedure.

While pregnancy itself is not considered to be an AE or SAE, any pregnancy complication or elective termination of a pregnancy will be reported as an AE or SAE. A spontaneous abortion is always considered to be an SAE and will be reported as such. Any post-study pregnancy related SAE considered reasonably related to the study treatment by the investigator will be reported to the sponsor as described in [Section 9.4.3](#). While the investigator is not obligated to actively seek this information in former study patients, he or she may learn of an SAE through spontaneous reporting.

CTCAE	Common Terminology Criteria for Adverse Events
C_{trough}	minimum concentration
CV	coefficient of variation
DLBCL	diffuse large B-cell lymphoma
DoR	duration of response
DSMC	Data Safety Monitoring Committee
ECG	electrocardiogram
ECOG	Eastern Cooperative Oncology Group
eCRF	electronic case report form
EMA	European Medicines Agency
ENR	Enrolled Participant Set
EOS	end of study
EOS EOT	end of study end of treatment
	·
ЕОТ	end of treatment
EOT FAS	end of treatment Full Analysis Set
EOT FAS FDA	end of treatment Full Analysis Set Food and Drug Administration
FAS FDA G-CSF	end of treatment Full Analysis Set Food and Drug Administration granulocyte colony-stimulating factor

Abbreviation	Term
ICF	informed consent form
ICH	International Council for Harmonisation of Technical Requirements for Pharmaceuticals for Human Use
INV	investigator
IPI	International Prognostic Index
IRR	infusion-related reaction
IV	intravenous(ly)
IWG	International Working Group
LEN	lenalidomide
MedDRA	Medical Dictionary for Regulatory Activities
MRI	magnetic resonance imaging
NA	not applicable
nAb	neutralizing antibody assay
NALT	nonstudy antilymphoma treatment
NCI	National Cancer Institute
NE	not evaluable
NHL	non-Hodgkin lymphoma
ORR	objective response rate
PAS	Primary Analysis Set
PD	progressive disease
PET	positron emission tomography
PFS	progression-free survival
PK	pharmacokinetic(s)
PKAS	Pharmacokinetic Analysis Set
PPS	Per-Protocol Set
PR	partial response
PT	preferred term
Q2W	once every 2 weeks
Q4W	once every 4 weeks
QTcB	QT interval corrected using Bazett's formula
QTcF	QT interval corrected using Fridericia's formula
R/R	relapsed/refractory
SAE	serious adverse event

Abbreviation	Term
SAF	Safety Analysis Set
SAP	Statistical Analysis Plan
SD	stable disease
SOC	system organ class
SPS	Screened Participants Set
TEAE	treatment-emergent adverse event
TLS	tumor lysis syndrome
WHO	World Health Organization

1. INTRODUCTION

This is an open-label, multicenter, Phase 1b/2 study to evaluate the safety and PK of tafasitamab IV combined with LEN in participants with R/R DLBCL. Section 3 of the Protocol provides a detailed description of the investigational products, target patient population, rationale for doses to be examined, and potential risks and benefits of treatment with tafasitamab and LEN.

The purpose of this SAP is to provide details of the statistical analyses that have been outlined in the MOR208C115 Protocol.

The structure and content of this SAP provide sufficient details to meet the requirements identified by the FDA, EMA, and ICH Guidance on Statistical Principles in Clinical Trials. All work planned and reported from this SAP will follow internationally accepted guidelines, published by the American Statistical Association and the Royal Statistical Society, for statistical practice.

The planned analyses identified in this SAP may be included in CSRs and/or in relevant summary report documents (eg, regulatory submissions or future manuscripts). Posthoc exploratory analyses not necessarily identified in this SAP may be performed to further examine study data and will not require an update to the final SAP. Any posthoc or unplanned exploratory analyses performed will be clearly identified as such and described in the CSR.

2. STUDY INFORMATION, OBJECTIVES, AND ENDPOINTS

2.1. Protocol and Case Report Form Version

This SAP is based on Protocol MOR208C115 v7.0 dated 11 APR 2024 and CRFs approved 10 JUL 2024. Unless superseded by an amendment, this SAP will be effective for all subsequent Protocol Amendments and eCRF versions.

In addition, ICH E9 (EMA 1998) and ICH E9 (R1; EMA 2020) will be the basis for the analysis strategies outlined in this SAP.

The reader of this SAP is encouraged to also read the clinical study Protocol, and other identified documents, for details on the design and planned conduct of this study. Operational aspects related to collection and timing of planned clinical assessments are not repeated in this SAP unless relevant to the planned analyses.

2.2. Study Objectives and Endpoints

Table 1 presents the objectives and endpoints.

Table 1: Objectives and Endpoints

 	Endpoints
Primary	
• To evaluate the safety and tolerability of tafasitamab administered in combination with LEN in participants with R/R DLBCL	Incidence and severity of TEAEs
• To determine a recommended dose for tafasitamab administration in combination with LEN in participants with R/R DLBCL	
Secondary	
•	Tafasitamab serum concentrations after 3 (C_{trough} and C_{max}) and 12 (C_{trough}) treatment cycles
To assess antitumor activity of tafasitamab doses in combination with LEN	• Best ORR by INV assessment up to Cycle 12 based on Cheson et al (2007)
•	• DoR by INV assessment based on Cheson et al (2007)
•	• PFS by INV assessment based on Cheson et al (2007)
C	Number and percentage of participants developing anti-tafasitamab antibodies up to Cycle 12

Note: Each treatment cycle is 28 days.

3. STUDY DESIGN

MOR208C115 (MINDway) is an open-label, multicenter, Phase 1b/2 study of tafasitamab combined with LEN to evaluate the safety and PK of tafasitamab tafasitamab in adult participants with R/R DLBCL.
Participants will receive LEN in combination with tafasitamab in 28-day cycles.
•
Lenalidomide 25 mg will be administered for a maximum of 12 cycles or until disease progression, unacceptable toxicity, withdrawal, death, or lost to follow-up, whichever occurs first. After Cycle 12 or LEN discontinuation, participants will continue with tafasitamab monotherapy until disease progression, unacceptable toxicity, withdrawal, death, or lost to follow-up, whichever occurs first.
participant discontinues the study for reasons other than safety before completion of the predefined safety observation window (5 weeks), the participant may be replaced.

A participant is considered to have started the study and entered the screening period when they have signed the ICF.

A participant is considered enrolled in the study if they receive at least 1 dose of study drug (tafasitamab or LEN).

The EOS is reached for an individual participant if any of the following applies: withdrawal, lost to follow-up, death, or completion of the EOS/90-day safety follow-up visit after treatment discontinuation. Regardless of the reason for treatment discontinuation (with the exception of withdrawal of consent, death, or lost to follow-up) all participants must complete a safety follow-up visit 90 days after the last dose of study treatment.

The EOS is reached when all participants still receiving study treatment have been followed for at least 3 years, or when the final participant on study has completed their last visit, whichever occurs first.

Overall survival follow-up after EOT will not be performed in the study.

3.1. Randomization

[figure not shown]
Not applicable.

3.2. Control of Type I Error

All statistical analyses are exploratory in nature. Unless otherwise specified, all CIs provided will be at the 95% confidence level.

3.3. Sample Size Considerations

As this is a Phase 1b/2 study, primary, secondary, and exploratory endpoints will be analyzed using descriptive statistics. No formal statistical tests will be performed.

3.4. Schedule of Assessments

Refer to Protocol v7.0 dated 11 APR 2024 for a full description of all study procedures and assessment schedules for this study.

3.5. Analysis Timepoints

3.5.1. Dose Escalation Analyses

A DSMC, consisting of sponsor and investigator representatives, will continuously monitor the study and can recommend stopping enrollment at any time based on emerging safety data.

. The DSMC recommendations will be guided by predefined safety criteria that apply to the 35-day safety observation window (from Cycle 1 Day 1 to Cycle 2 Day 7). Details of the predefined safety criteria can be found in Protocol Section 5.2.

Details of specific responsibilities, composition, and meeting formats and frequency of the DSMC are outlined in the DSMC charter.

3.5.2. Primary Completion Analysis

The primary completion analysis will be performed when all participants have either reached Cycle 3 Day 28 or discontinued study treatment prior to Cycle 3 Day 28.

Primary and secondary objectives will be analyzed at the time of the primary completion analysis. Additional analyses for safety or efficacy endpoints may be performed if needed or if requested by authorities.

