##### 10.3.1.1 Primary Analysis

Primary analysis will be performed when all patients have either reached C3D28 or discontinued the study prior to C3D28.

Primary and Secondary Objectives will be analyzed at the time of primary analysis completion. Details will be provided in the SAP.

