7.3. Analysis of the Secondary Efficacy Parameter(s)

7.3.1. Endpoint: Objective Response Rate

The ORR is defined as the proportion of participants with CR or PR as the best response achieved at any time during the study. Only responses of CR or PR that were documented before the initiation of NALT will be considered. The denominator will be the total number of participants included in the analysis set.

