7.3.1.1. Main Estimand Analysis

The estimand of ORR, with its 5 attributes and the strategies for addressing the defined intercurrent events, is presented in Table 5.

Table 5: Estimand of Objective Response Rate

Estimand Attribute		Definition		
Treatment	Tafasitamab in combination with LEN administered for up to 12 cycles in total, after which participants can continue with tafasitamab as monotherapy.			
Population		All participants with R/R DLBCL as per eligibility criteria who received at least 1 dose of tafasitamab and 1 dose of LEN		
Variable	ORR			
Intercurrent events	Event	Strategy	Rationale (if needed)	
	No postbaseline response assessment or not adequately assessed (eg, NE)	Hypothetical strategy	Participant will be considered as nonresponder	
	Treatment discontinuation due to any reason	Treatment policy	All responses will be considered regardless of treatment discontinuation	
	Death without postbaseline assessment or not adequately assessed (eg, NE)	Hypothetical strategy	Participant will be considered as nonresponder	
	Start of any NALT	While on treatment strategy	Only response prior to the start of any new antilymphoma therapies will be considered	
	Study withdrawal due to any reason during the post-treatment disease follow-up	While on treatment strategy	All responses will be considered up to study withdrawal	
Population-level summary	Percentage and 95% CI us	sing the Clopper-Pearson n	nethod	

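### At the primary completion analysis the Cycle 12 rates (best ORR, ADA incidence) can only be biased low, because participants still short of Cycle 12 without a response or positive sample count as negative

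*SAP*

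**What the plan says.** SAP 3.5.2 sets the trigger at the point "when all participants have either reached Cycle 3 Day 28 or discontinued study treatment prior to Cycle 3 Day 28". It then states: "Primary and secondary objectives will be analyzed at the time of the primary completion analysis". Protocol 10.3.1.1 says the same: "Primary and Secondary Objectives will be analyzed at the time of primary analysis completion". Neither document defers any secondary endpoint.

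The objectives tables (Protocol Table 1 and SAP Table 1) end the window for two secondary endpoints at Cycle 12. One is best ORR by investigator assessment. The other is immunogenicity: "Number and percentage of participants developing anti-tafasitamab antibodies up to Cycle 12".

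The analysis rules set no minimum follow-up:

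- **ORR (SAP 7.3.1):** "The denominator will be the total number of participants included in the analysis set". The set is the FAS (7.3.1.2). CR or PR counts if documented before non-study lymphoma treatment. For no post-baseline assessment, or none that is adequate, Table 5 says: "Participant will be considered as nonresponder".
- **ADA (SAP 5.3.9 and 9.2):** the set is the IAS, meaning at least one tafasitamab dose and one valid ADA assessment. A participant is without antibodies if every sample after C1D1 is negative, however many have been taken.

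SAP 3.5.3 repeats the analyses on updated data about 3 years after the last enrolment.

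**The concern.** The trigger falls nine cycles before the end of the window that defines these two endpoints. Best response and ever-positive ADA status can only move upward with further follow-up. A participant with stable disease at the first scan who responds at the second, or whose first positive ADA sample comes at Cycle 6, enters the first report as a negative. No rule sets such participants apart.

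The report will give an ORR with an exact 95% CI and an ADA percentage, overall and by treatment group. The CI covers sampling error only and does not reflect incomplete follow-up. Until the final analysis this is the only scheduled readout of both endpoints, and nothing in the SAP labels it preliminary. Enrolment runs through two sequential cohorts and then an expansion at the recommended dose, so dose groups may also differ in how long their participants could have been observed.

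**Working it through.** The plan contains no precision or power figure for ORR or ADA, so there is none to reproduce. The one related figure that can be checked is the L-MIND ORR in Protocol 3.3.2: 46/80 = 57.5%, with a Clopper-Pearson interval of 45.9% to 68.5%, as printed.

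**1. Calendar.** Study day = (cycle − 1) × 28 + day.

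- C3D28 = 2 × 28 + 28 = 84
- C12D28 = 11 × 28 + 28 = 336
- Gap = 336 − 84 = 252 days; 252 / 30.4375 = 8.3 months

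**2. What the last participant has contributed by day 84** (Protocol Table 3 and its footnotes).

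- Response assessments are tied to C3D1 (day 57), C5D1 (113), C7D1 (169), C10D1 (253) and C12D28 (336): 1 of 5 done.
- Post-baseline ADA samples fall at C2D1 (day 29), C3D1 (57), C4D1 (85), C6D1 (141), C8D1 (197), C10D1 (253), C12D1 (309) and C12D28 (336): 2 of 8 done.

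**3. Share whose potential follow-up is short of C12D28.** The accrual period is not stated, so uniform accrual over A days is assumed. Share = 252 / A.

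**4. Effect on ORR.** Further assumptions: a final ORR of 57.5% (an independently reviewed L-MIND figure, borrowed here for an investigator-assessed rate) and two patterns of first response across the five assessments, 80/10/5/3/2% and 55/20/12/8/5%. The CT scans come just before the named visits, so they are credited at days 56, 112, 168 and 252, and the C12D28 scan at day 336.

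Participants short of Cycle 12 fall into four bands of potential follow-up: days 84–112 (28 days wide), 112–168 (56), 168–252 (84) and 252–336 (84). The widths sum to 252. Shortfall = 57.5 × Σ(band width × fraction of responders not yet detected) / A.

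- 80% pattern: 28 × 0.20 + 56 × 0.10 + 84 × 0.05 + 84 × 0.02 = 17.08
- 55% pattern: 28 × 0.45 + 56 × 0.25 + 84 × 0.13 + 84 × 0.05 = 41.72

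| Accrual | A (days) | Short of Cycle 12 (of 51) | Shortfall, 80% pattern | Shortfall, 55% pattern |
|---|---|---|---|---|
| 12 months | 365.25 | 69% (about 35) | 2.7 points | 6.6 points |
| 18 months | 547.875 | 46% (about 23) | 1.8 | 4.4 |
| 24 months | 730.5 | 34% (about 18) | 1.3 | 3.3 |
| 30 months | 913.125 | 28% (about 14) | 1.1 | 2.6 |

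The reported overall ORR would thus be about 51% to 56% instead of 57.5%. Among only those short of Cycle 12, the shortfall is 57.5 × 17.08 / 252 = 3.9 points to 57.5 × 41.72 / 252 = 9.5 points. A separate calculation with slower response (40% detected at the first scan) and accrual of 12 to 36 months widens the overall range to about 1 to 9 points.

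**5. ADA.** The direction is the same. The documents give neither an expected incidence nor a time course of antibody formation, so no size can be computed.

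**The case against.** The case on the other side has real weight.

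- **Response to date is conventional.** Reporting it in a single-arm, descriptive trial and updating it later is common practice. The primary endpoint is TEAEs, and the DSMC is guided by 35-day safety criteria. No visible decision rests on this ORR. This limits the importance of the point but does not remove the bias.
- **The complete result is planned.** True. The problem is confined to the primary completion report.
- **Maturity is partly disclosed.** SAP 6.2.3 gives first and last enrolment dates, 7.3.1.2 swimmer plots, 7.3.4 PFS follow-up, and 9.2 missing ADA counts per visit. The PFS follow-up covers only the overall group and the recommended dose, and none of these changes the ORR or ADA estimate or its interval.
- **The shift is small against sampling error.** At 29/51 the exact interval is 42% to 71%. That is fair, but a bias with a known direction is a separate matter from an interval's width.
- **SAP 7.3.1 uses an open window,** the "proportion of participants with CR or PR as the best response achieved at any time during the study". That makes a day-84 trigger less mature still. The conflict with the Cycle 12 window is a separate matter to reconcile.

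Two stronger readings are tempting and fail. A reader might infer that everyone short of Cycle 12 is counted as a nonresponder. At 12-month accrual that would take the ORR to 57.5 × (1 − 0.69) = 18%. The SAP does not do this: any CR, PR or positive sample already documented counts in whatever cycle it occurs, and a participant whose disease has progressed without response is already a settled nonresponder. The shares in the table are therefore not misclassification shares.

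A reader might also infer that the recommended dose is shown to be the one understated. The enrolment order suggests that the expansion is the least mature group. Cohort details are redacted, however, and if the recommended dose is that of the first cohort, early participants belong to the same group.

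**Conclusion.** The concern holds in limited form. At the primary completion analysis, participants who are short of Cycle 12 and have no response or positive ADA sample yet are counted as negative, so both rates are biased low against their stated endpoints unless nobody first responds or seroconverts after the cutoff. The timing mismatch and the direction follow from the text alone. The size does not: about 1 to 7 points on the overall ORR depends on assumed uniform accrual of 51 participants over 12 to 30 months, a final ORR of 57.5%, and 55 to 80% of responders detected at the first scan. No ADA magnitude is available, and a concentration at the recommended dose is plausible but unproven. The final analysis is unaffected. The change is worth making because it is cheap and the bias runs one way.

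**What to change.** Amend SAP 3.5.2, 7.3.1.2 and 9.2 as follows:

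- Keep the whole-FAS ORR and whole-IAS ADA results at the primary completion cutoff, label them interim, and show median potential follow-up by dose group beside them.
- Add a supportive ORR and ADA estimate limited to FAS/IAS participants whose Cycle 1 Day 1 is at least 340 days before the data cutoff (336 plus the 4-day imaging window at C12D28), whether or not they are still on treatment.
- Select by enrolment date. Selecting those who reached Cycle 12 or discontinued would keep recent early failures while dropping recent participants still on treatment, and would bias the ORR low again.
- Note that cycle delays allowed under Protocol 7.3.3 mean a few selected participants may still be short of C12D28.
- State that the final analysis is definitive for the Cycle 12 endpoints.

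The cost is SAP wording and one extra denominator in the ORR and ADA tables, with no new data or visits. The drawback is precision: under the accrual assumptions above the restricted estimate would rest on roughly 16 (51 − 35) to 37 (51 − 14) participants, with a correspondingly wider interval. For that reason it should supplement the whole-set result and not replace it.
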